8.4 EXPEDITED REPORTING OF ADVERSE EVENTS

BI is responsible to fulfil their legal and regulatory reporting obligation in accordance with regulatory requirements.

Exemptions from expedited reporting are described in Section 5.2.6.2.5, if applicable.

8.5 STATEMENT OF CONFIDENTIALITY AND PATIENT PRIVACY

Individual patient data obtained as a result of this trial is considered confidential and disclosure to third parties is prohibited with the exceptions noted in Section 8.7.

Data protection and data security measures are implemented for the collection, storage and processing of patient data in accordance with the principles 6 and 12 of the WHO GCP handbook.

Personalised treatment data may be given to the patient's personal physician or to other appropriate medical personnel responsible for the patient's welfare. Data generated at the site as a result of the trial need to be available for inspection on request by the participating physicians, the sponsor's representatives, by the IRB / IEC and the regulatory authorities.

8.5.1 Collection, storage and future use of biological samples and corresponding data

Measures are in place to comply with the applicable rules for the collection, biobanking and future use of biological samples and clinical data, in particular

- Sample and data usage has to be in accordance with the separate biobanking informed consent
- The BI-internal facilities storing biological samples from clinical trial participants as well as the external banking facility are qualified for the storage of biological samples collected in clinical trials.
- An appropriate sample and data management system, incl. audit trail for clinical data and samples to identify and destroy such samples according to ICF is in place
- A fit for the purpose documentation (biomarker proposal, analysis plan and report) ensures compliant usage
- A fit for purpose approach will be used for assay/equipment validation depending on the intended use of the biomarker data
- Samples and/or data may be transferred to third parties and other countries as specified in the biobanking ICF

8.6 TRIAL MILESTONES

Independent milestones will be defined in each individual Module. Milestones for the Master are not necessary since it is the launching point for each Module.

The start of the trial is defined as the date when the first patient in the whole trial signs informed consent for the Master protocol and treatment-specific Module.

The **end of the trial** is defined as the date of the last visit of the last patient in the whole trial ('Last Patient Completed').

The '**Last Patient Last Treatment**' (LPLT) date is defined as the date on which the last patient in the whole trial is administered the last dose of trial treatment (as scheduled per protocol or prematurely). Individual investigators will be notified of SUSARs occurring with the trial medication until 30 days after LPLT at their site.

Early termination of the trial is defined as the premature termination of the trial due to any reason before the end of the trial as specified in this protocol.

Temporary halt of the trial is defined as any unplanned interruption of the trial by the sponsor with the intention to resume it.

Suspension of the trial is defined as an interruption of the trial based on a Health Authority request.

8.7 ADMINISTRATIVE STRUCTURE OF THE TRIAL

The trial is sponsored by Boehringer Ingelheim (BI).

A Coordinating Investigator is responsible to coordinate investigators at the different sites participating in this trial. Tasks and responsibilities are defined in a contract.

A Steering Committee (SC) consisting of independent experts and sponsor representatives will be established to support the Coordinating Investigator who will be the chair of the SC. The composition of the SC will be documented in the Trial Master File (TMF). The tasks and responsibilities will be agreed in contracts between the SC members and the sponsor and also summarised in a SC charter.

The safety of all patients will be under surveillance by the Safety Review Committee (SRC). The SRC will be responsible for assessing the progress of the clinical trial, including making safety and efficacy assessments at specified intervals. The SRC will have unblinded access to data from this trial.

Members of the SRC will include:

- [REDACTED] Medical Monitor for the trial
- Principal Investigators, or delegates, from investigational sites
- BI Safety Physician, or delegate
- BI Clinical Program Leader responsible for the project
- BI Project or Trial Statistician.

The BI Safety Physician, BI Clinical Program Leader, or delegate, should always attend the SRC, if there are safety issues for discussion. [REDACTED], [REDACTED], Medical Monitor, or delegate, should always be present at the SRC.

The tasks and responsibilities of the SRC will be documented. The SRC will maintain written records of all its meetings.

Relevant documentation on the participating (Principal) Investigators (e.g. their curricula vitae) will be filed in the ISF.

Data Management and Statistical Evaluation will be done by BI according to BI SOPs.

Tasks and functions assigned in order to organise, manage, and evaluate the trial are defined according to BI SOPs. A list of responsible persons and relevant local information can be found in the ISF.

An IRT vendor will be used in this trial. Details will be provided in the IRT Manual are available in the ISF.

10. APPENDICES

10.1 IMMUNE-RELATED ADVERSE EVENTS OF SPECIAL INTEREST

Table 10.1: 1 Immune-related adverse events of special interest

This table defines immune-related AEs that must be reported as AESIs.

Immune-related adverse events of special interest
Pneumonitis (reported as an AESI if \geq Grade 2) 
• Acute interstitial pneumonitis• Interstitial lung disease• Pneumonitis
Colitis (reported as an AESI if \geq Grade 2 or any grade resulting in dose modification or use of systemic steroids to treat the AE) 
• Intestinal obstruction• Colitis• Colitis microscopic• Enterocolitis• Enterocolitis haemorrhagic• Gastrointestinal perforation• Necrotizing colitis• Diarrhoea
Endocrine (reported as an AESI if \geq Grade 3 or \geq Grade 2 and resulting in dose modification or use of systemic steroids to treat the AE) 
• Adrenal insufficiency• Hyperthyroidism• Hypophysitis• Hypopituitarism• Hypothyroidism• Thyroid disorder• Thyroiditis• Hyperglycaemia, if \geq Grade 3 and associated with ketosis or metabolic acidosis
Endocrine (reported as an AESI) 
• Type 1 diabetes mellitus (if new onset)

Immune-related adverse events of special interest

Hematologic (reported as an AESI if \geq Grade 3 or any grade resulting in dose modification or use of systemic steroids to treat the AE)

- Autoimmune haemolytic anaemia
- Aplastic anaemia
- Thrombotic thrombocytopenic purpura
- Idiopathic (or immune) thrombocytopenia purpura
- Disseminated intravascular coagulation
- Haemolytic-uraemic syndrome
- Any Grade 4 anaemia regardless of underlying mechanism

Hepatic (reported as an AESI if \geq Grade 2, or any grade resulting in dose modification or use of systemic steroids to treat the AE)

- Hepatitis
- Autoimmune hepatitis
- Transaminase elevations (ALT and/or AST)

Infusion Reactions (reported as an AESI)

- Allergic reaction
- Anaphylaxis
- [REDACTED] release syndrome
- Serum sickness
- Infusion reactions
- Infusion-like reactions

Neurologic (reported as an AESI)

- Autoimmune neuropathy
- Guillain-Barre syndrome
- Demyelinating polyneuropathy
- Myasthenic syndrome

Ocular (report as an AESI if \geq Grade 2 or any grade resulting in dose modification or use of systemic steroids to treat the AE)

- Uveitis
- Iritis

Renal (reported as an AESI if \geq Grade 2)

- Nephritis
- Nephritis autoimmune
- Renal failure
- Renal failure acute
- Creatinine elevations (report as an irAE if \geq Grade 3 or any grade resulting in dose modification or use of systemic steroids to treat the AE)

Immune-related adverse events of special interest

Skin (reported as an AESI)

- Dermatitis exfoliative
- Erythema multiforme
- Stevens-Johnson syndrome
- Toxic epidermal necrolysis

Skin (reported as an AESI if \geq Grade 3)

- Pruritus
- Rash
- Rash generalized
- Rash maculopapular
- Any rash considered clinically significant in the physician's judgment

Other (reported as an AESI)

- Myocarditis
- Pancreatitis
- Pericarditis
- Any other Grade 3 event that is considered immune-related by the physician

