5.2.6.2 Adverse event collection and reporting

5.2.6.2.1 AE Collection

The investigator shall maintain and keep detailed records of all AEs in the patient files. The following must be collected and documented on the appropriate CRF(s) by the investigator:

- From signing the ICF onwards until the end of treatment (including the residual effect period (REP); a period of 30 days after the last dose of trial medication) - all AEs (non-serious and serious) and all AESIs.
- After the end of treatment, including REP until the individual patient's end of trial - all related SAEs and all related AESIs and any occurrence of cancer of new histology.
- After the individual patient's end of trial, the Investigator does not need to actively monitor the patient for new AEs but should only report related SAEs and related AESIs and any occurrence of cancer of a new histology of which the investigator may become aware of by any means of communication, e.g. phone call. Those AEs should however, not be reported in the CRF.

The rules for AE reporting exemptions still apply, please see Section [5.2.6.2.5](#).

All AEs which occurred through the treatment phase and throughout the REP will be considered as on treatment; please see Section 7.3.4. Events which occurred after the REP will be considered as post-treatment events.

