5.2.6.2.5 Exemptions to AE/SAE reporting

Disease progression is a trial endpoint for analysis of efficacy and as such is exempted from reporting as an AE or SAE. Progression of the subject's underlying malignancy will be recorded on the appropriate pages of the eCRF as part of efficacy data collection only and will not be reported on the SAE Form. It will therefore not be entered in the safety database (ARISg) and hence not get expeditiously reported. Death due to disease progression is also to be recorded on the appropriate eCRF page and not on the SAE Form. However, when there is evidence suggesting a causal relationship between the study drug or study drugs and the progression of the underlying malignancy, the event must be reported as an SAE on the SAE Form and on the eCRF.

Examples of exempted events of PD may be:

[figure not shown]
- Progression of underlying malignancy (progressive disease [PD]): if PD is clearly consistent with the suspected progression of the underlying malignancy as defined by the respective response criteria.
- Hospitalisation/procedures due solely to the progression of underlying malignancy (PD)
- Clinical symptoms and/or signs of progression (without confirmation by objective criteria e.g., imaging, clinical measurement): if the symptom can exclusively be determined to be due to the progression/relapse of the underlying malignancy and does meet the expected pattern of progression for the disease under study.

Exempted events are collected and tracked following a protocol specified monitoring plan. Exempted events are monitored at appropriate intervals throughout the study at Safety Review Meetings.

Lab values meeting the hepatic injury definition as defined in Section [5.2.6.1.3](#) will need to be reported as AESI. PD reporting exemption does not apply to hepatic injury.

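### Grade 4 anaemia attributed to progression is a mandatory AESI in Table 10.1: 1 but can be exempt from reporting under section 5.2.6.2.5

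*Protocol*

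**What the plan says.** Four parts of the Master protocol bear on the point.

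- **Appendix 10.1, Table 10.1: 1.** The table opens with "This table defines immune-related AEs that must be reported as AESIs". Its haematologic block ends with "Any Grade 4 anaemia regardless of underlying mechanism".
- **Section 5.2.6.2.1 (AE Collection).** From consent to the end of the residual effect period, sites must collect "all AEs (non-serious and serious) and all AESIs". After the list of collection periods the section adds: "The rules for AE reporting exemptions still apply".
- **Section 5.2.6.2.5 (Exemptions).** The general rule is "Disease progression is a trial endpoint for analysis of efficacy and as such is exempted from reporting as an AE or SAE". The examples include clinical signs and symptoms of progression, "if the symptom can exclusively be determined to be due to the progression/relapse of the underlying malignancy", provided that they also match the pattern expected for the disease. Progression is kept off the SAE form and out of the safety database, so it is not expedited. Two things are taken back out of the exemption. Progression that may have been caused by study drug must be reported as an SAE, and for liver findings the section ends with "PD reporting exemption does not apply to hepatic injury".
- **Sections 5.2.6.1.3 and 5.2.6.2.2.** An AESI is defined as a particular kind of AE. It is reported on the same form as an SAE and within the same 24 hours.

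**The concern.** The anaemia row is worded to remove any judgement about cause, while the exemption depends on a judgement about cause. Where the site decides that a Grade 4 anaemia is due only to the tumour, both rules apply to the same event and give opposite instructions.

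What is at stake is the completeness of the AESI data and of 24-hour reporting for one severe event type. Two sites with the same case could act differently and each cite the protocol. The AESI tables would then mix two practices, and nothing in the protocol or the SAP supplied would let a reader separate them. Protocol section 7.3.4 does not say how exempted events are tabulated. SAP section 7.8 refers back to 7.3.4, and SAP section 7.8.1 refers to the Master TSAP.

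**Working it through.** There is no figure to reproduce, since the point concerns reporting rules. The check is to follow one case through the text: a treated patient, within the residual effect period, has Grade 4 anaemia that the investigator attributes solely to progression and that fits the expected course of the disease.

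1. **Is it in Table 10.1: 1?** Yes. The anaemia row applies whatever the cause, so tumour-related anaemia is included. The table's opening line makes reporting mandatory.
2. **Can it be a sign of the kind that 5.2.6.2.5 exempts?** Yes. Section 5.2.6.1 counts an abnormal laboratory finding as a sign. By construction the case meets both conditions of the exemption: attribution exclusively to progression, and expected pattern.
3. **Does the exemption reach AESIs?** Section 5.2.6.2.5 names AEs and SAEs but not AESIs. Three features of the text still extend it to them:
   - Section 5.2.6.1.3 defines an AESI as a specific type of AE, so an event that is exempt as an AE has no separate route to AESI status.
   - Section 5.2.6.2.1 states the collection rule for all AESIs and then says that the exemptions still apply.
   - Section 5.2.6.2.2 sends AESIs on the SAE form, and 5.2.6.2.5 keeps progression off that form.
4. **Is there an exception that rescues it?** The hepatic exception does not cover anaemia. The drug-causation exception covers progression suspected to be caused by study drug, which is a different case. Hepatic injury is the only AESI category named, which suggests that the authors saw a need to say so expressly for an AESI.
5. **Does any section set precedence?** No supplied section says whether the table row or the exemption prevails.

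| | Table 10.1: 1 | Section 5.2.6.2.5, via 5.2.6.2.1 |
|---|---|---|
| Status of the event | AESI | Exempt as progression |
| SAE form within 24 hours | Required | Not used |
| Safety database | Entered | Not entered |
| Tracking at Safety Review Meetings | Not the stated route | Yes |
| Haemoglobin in laboratory summaries (5.2.3, 7.3.4) | Yes | Yes |

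The last two rows limit what could be lost. The low haemoglobin value stays visible either way. Under the exemption, the AESI report, its causality assessment and its expedited notification may be missing.

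The conflict is confined to the period from consent to the end of the residual effect period. After that, 5.2.6.2.1 asks only for related AESIs, and an anaemia judged to be due solely to progression would not be one.

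**The case against.** The best answer is that a specific rule prevails over a general one. The anaemia row was written for this event and disregards cause, while the exemption is general and does not mention AESIs. In addition, the Amendment 1 log describes the hepatic sentence as a clarification, which might suggest that AESIs were already thought to lie outside the exemption. This reading is available to a site, but the protocol does not state it. It also sits badly with the definition of an AESI as an AE, with the reminder in 5.2.6.2.1, and with a closing sentence that names hepatic injury alone. The ambiguity therefore remains.

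Several limiting points stand in full. The exemption is narrow, because it needs both exclusive attribution and the expected pattern. Exempted events are still collected under a monitoring plan and reviewed. Attribution by an investigator who knows the treatment follows from the open-label design and is not a separate defect. The Module C protocol and the Master TSAP were not among the documents. Since 5.2.6.1.3 allows Modules to define AESIs, a resolution there cannot be excluded.

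A reader might also infer more than the text supports:

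- **That the whole table conflicts with the exemption**, for example intestinal obstruction, perforation, renal failure or disseminated intravascular coagulation. The table is limited to immune-related events, and only the anaemia row sets cause aside. An obstruction due solely to tumour is not immune-related, so for those rows the two sections need not collide.
- **That the exemption halves the Grade 4 rate.** Section 1.4 reports Grade 4 AEs in 4.0% of 50 patients (0.04 × 50 = 2), one recorded as disease progression and one as sepsis. Removing the first gives 1/50 = 2%. That event is not a Table 10.1: 1 term, comes from another trial, and would stay exempt after the fix. Neither of the two was anaemia.

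**Conclusion.** The inconsistency is real and specific to one row. A Grade 4 anaemia attributed exclusively to progression is a mandatory 24-hour AESI under Table 10.1: 1 and can be exempt under 5.2.6.2.5 read with 5.2.6.2.1. AESI tables and expedited reporting for this event may therefore be incomplete or inconsistent between sites.

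No size can be given. The documents contain neither a rate of Grade 4 anaemia on the combination nor the share that sites would attribute to progression. A claim that the reported rates are biased low is not supported either: it would require sites to follow the exemption rather than the table, and the text does not settle which they should follow.

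The conclusion assumes that neither the Module C protocol nor the Master TSAP already resolves the precedence. The point concerns safety reporting and does not touch the efficacy analyses.

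**What to change.** Reconcile sections 5.2.6.2.1 and 5.2.6.2.5 with Table 10.1: 1. The simplest way is to extend the last sentence of 5.2.6.2.5, on the model of the hepatic exception. Suggested wording: *The PD reporting exemption does not apply to hepatic injury or to Grade 4 anaemia as listed in Table 10.1: 1; progression may be recorded as the cause.* The existing cross-reference in 5.2.6.2.1 then leads sites to the right rule without further change.

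A blanket exception for every Table 10.1: 1 term is not needed. It would bring tumour-caused events into a list meant for immune-related ones. If a Module already settles the matter, a cross-reference to it in 5.2.6.2.5 is enough.

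The cost is one sentence in the Master protocol and an occasional extra AESI form for an anaemia that the site attributes to the tumour.

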5.2.6.1.1 Serious adverse event

A serious adverse event (SAE) is defined as any AE, which fulfils at least one of the following criteria:

- results in death,
- is life-threatening, which refers to an event in which the patient was at risk of death at the time of the event; it does not refer to an event that hypothetically might have caused death if more severe,
- requires inpatient hospitalisation,
- requires prolongation of existing hospitalisation,
- results in persistent or significant disability or incapacity,
- is a congenital anomaly / birth defect,
- is deemed serious for any other reason if it is an important medical event when based on appropriate medical judgement which may jeopardise the patient and may require medical or surgical intervention to prevent one of the other outcomes listed in the above definitions. Examples of such events are intensive treatment in an emergency room or at home for allergic bronchospasm, blood dyscrasias or convulsions that do not result in hospitalisation or development of dependency or abuse.

Patients may be hospitalised for administrative reasons during the trial, including hospitalisation for respite care. These as well as hospitalisations/surgical procedures which were planned before the patient signed informed consent need not be reported as SAEs if they have been documented at or before signing of the informed consent and have been performed as planned (the condition requiring hospitalisation/surgical procedure has not changed/worsened after signing informed consent).

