5.2.6.1.3 Adverse events of special interest

The term adverse events of special interest (AESI) relates to any specific AE that has been identified at the project level as being of particular concern for prospective safety monitoring and safety assessment within this trial, e.g. the potential for AEs based on knowledge from other compounds in the same class. AESIs need to be reported to the sponsor's Pharmacovigilance Department within the same timeframe that applies to SAEs, please see Section 5.2.6.2.2.

For this trial, infusion-related AEs, potential DILI events, hepatic injury, and qualifying irAEs, as defined in the treatment-specific Modules and Appendix [10.1](#), are AESIs.

Immune-related adverse events (irAEs)

Immune-related AEs are AEs associated with immunotherapy treatments that appear to be associated with the immune therapy's mechanism of action. These adverse reactions, which can be severe, may involve the gastrointestinal, skin, liver, endocrine, respiratory, renal, or other organ systems. All immune-related events are to be reported as AEs. Some irAEs also need to be reported as AESIs as defined by the sponsor in Appendix [10.1](#). If an Investigator determines a Grade 3 event of an AE that is not mentioned on the list of immune-related AEs, the Investigator should also report that event as an AESI.

Recommendations for the management of irAEs are presented in Appendix [10.2](#).

Infusion-related reactions

In the event of an infusion-related reaction \leq Grade 2, treat the symptoms accordingly with antihistamine or corticosteroids if needed. The infusion rate of ezabenlimab may be decreased by 50% or interrupted until resolution of the event and re-initiated at 50% of the initial rate until completion of the infusion. In patients experiencing infusion-related reactions \leq Grade 2, subsequent infusions may be administered at 50% of the initial rate. If an infusion-related reaction to trial medications is Grade 3 or higher in severity at any point during the study, permanently discontinue study drug(s).

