 - Ezabenlimab should be permanently discontinued for Grade 4 rash, any recurrent Grade 3 AE or persistent Grade 2-3 AEs that do not recover to Grade 1 or less within 12 weeks.
- Encephalitis
 - Ezabenlimab should be permanently discontinued for any grade encephalitis.
- Infusion reactions:

Signs and symptoms usually develop during or shortly after drug infusion and generally resolve completely within 24 hours of completion of infusion. In the event of an infusion-related reaction \leq Grade 2, treat the symptoms accordingly with antihistamine or corticosteroids if needed, the infusion rate of study drug(s) may be decreased by 50% or interrupted until resolution of the event and re-initiated at 50% of the initial rate until completion of the infusion. In patients experiencing infusion-related reactions \leq Grade 2, subsequent infusions may be administered at 50% of the initial rate. If an infusion-related reaction is Grade 3 or higher in severity at any point during the study, permanently discontinue study drug(s).

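### The AESI catch-all stops at Grade 3 and encephalitis is not on the AESI list, so a small group of non-serious immune-related events misses the 24-hour report and, if late, is not collected

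*Protocol*

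**What the plan says.** Table 10.1: 1 (protocol Section 10.1) lists the immune-related events to be reported as AESIs. Its final row, headed Other, ends with "Any other Grade 3 event that is considered immune-related by the physician". Section 5.2.6.1.3 has a matching sentence that begins "If an Investigator determines a Grade 3 event of an AE that is not mentioned on the list of immune-related AEs" and has that event reported as an AESI as well.

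Elsewhere the table marks an open-ended grade explicitly. One row reads "Skin (reported as an AESI if \geq Grade 3" (the extracted text shows the greater-or-equal sign as a code). The endocrine and hematologic rows and the creatinine entry also use Grade 3 or higher.

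The row "Neurologic (reported as an AESI" carries no grade threshold and names four terms: autoimmune neuropathy, Guillain-Barre syndrome, demyelinating polyneuropathy and myasthenic syndrome. Encephalitis is not among them or in any other row. Section 10.2 nevertheless states, "Ezabenlimab should be permanently discontinued for any grade encephalitis", and says the same in its opening paragraph.

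Section 5.2.6.2.1 collects all AEs and AESIs from consent to the end of the residual effect period (REP), which is 30 days after the last dose. From then to the patient's end of trial it collects only "all related SAEs and all related AESIs and any occurrence of cancer of new histology". Section 5.2.6.2.2 sets one 24-hour timeline for SAEs and AESIs alike.

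**The concern.** Read literally, an unlisted immune-related event is an AESI at Grade 3 and stops being one at Grade 4. Nothing in the protocol explains that inversion, and because other rows of the table do write Grade 3 or higher, the bare wording reads as a limit.

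The absence of encephalitis is a similar mismatch. Several rows make an event an AESI at any grade once it leads to dose modification or systemic steroids. Encephalitis ends ezabenlimab at any grade and yet is not listed.

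AESI status decides two things for an event that is not serious: whether the sponsor hears of it within 24 hours, and whether it is collected at all once the REP is over. Immune-related events can start after treatment has stopped, so the second matters for the completeness of the late safety data.

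**Working it through.** No figure in the plan is at issue. The check is to take each kind of event through the AESI list (5.2.6.1.3, Table 10.1: 1), the seriousness criteria (5.2.6.1.1), the collection windows (5.2.6.2.1) and the reporting timeline (5.2.6.2.2).

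Two seriousness criteria matter most. An AE is an SAE if it "results in death" or "is life-threatening, which refers to an event in which the patient was at risk of death at the time of the event". The others are hospitalisation or its prolongation, disability, congenital anomaly, and an important medical event on medical judgement. None is defined by CTCAE grade. The protocol cites CTCAE version 5 without reproducing its definitions, so I assume that Grade 5 means death and that some Grade 4 events, such as those graded on a laboratory value alone, need not be serious.

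| Event | AESI in the Master text? | SAE? | 24-hour report | Collected if it starts after the REP (related) |
|---|---|---|---|---|
| Unlisted immune-related, Grade 3 | Yes, by the catch-all | Either | Yes | Yes |
| Unlisted immune-related, Grade 4, serious | No | Yes | Yes | Yes |
| Unlisted immune-related, Grade 4, not serious | No | No | **No** | **No** |
| Unlisted immune-related, Grade 5 | No | Yes | Yes | Yes |
| Encephalitis, serious, any grade | Not listed | Yes | Yes | Yes |
| Encephalitis, Grade 3, not serious, judged immune-related | Yes, by the catch-all | No | Yes | Yes |
| Encephalitis, Grade 1-2 (or Grade 4), not serious | No | No | **No** | **No** |

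The gap is the third and the last row. If such an event starts before the end of the REP it is still recorded in the CRF as an AE, and only the expedited report is missing. If it starts later it is not collected.

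For size, the only data in the documents are in Section 1.4: 50 patients on ezabenlimab monotherapy in trial 1381.1. Grade 4 AEs occurred in 4.0%, that is 0.04 × 50 = 2 patients (one disease progression, one sepsis), and neither was considered related. The only Grade 3 immune-related event was an AST increase, which the table already lists. So 0 of 50 had a related Grade 4 event, which is compatible with a true rate of up to 1 − 0.05^(1/50) = 5.8% (one-sided 95% bound). Only non-serious, unlisted events within that rate would fall in the gap. These data are from monotherapy, not the combinations, and do not measure onset after the REP.

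**The case against.** The strongest reply is that the SAE route already does the work. A reader might infer that every unlisted Grade 4 or 5 immune-related event, and all non-serious encephalitis, escapes expedited reporting and late collection. The documents do not support that. Fatal, life-threatening, hospitalised or disabling events are SAEs, follow the same 24-hour timeline and, if related, are collected after the REP. Non-serious Grade 3 encephalitis judged immune-related falls within the catch-all.

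The important-medical-event criterion also reaches some of the remainder, and its examples include blood dyscrasias and convulsions without hospitalisation. It rests on judgement, so it narrows the gap without closing it. Two sources that were not available could narrow it further: the sponsor's Always Serious list (5.2.6.1.2) and the Module-specific AESI definitions (5.2.6.1.3). Many obvious candidates are already listed, among them transaminase elevations, pancreatitis and Grade 4 anaemia. That last entry cuts both ways, since for one Grade 4 event the table does not rely on the SAE route alone.

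A reader might also infer that AESI tables would show Grade 3 events and leave out the more severe ones. No AESI table is specified in the documents supplied. The Module C SAP refers AE analysis to the Master TSAP, which was not available, and protocol Section 7.3.4 tabulates treatment-emergent AEs by frequency and severity, so Grade 4 and 5 events up to the end of the REP would appear there.

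Finally, AESIs are chosen at project level and Section 10.2 is management guidance, so the two lists need not match in every entry. That is fair as a general point. It does not explain why encephalitis is left out of a Neurologic row that has no grade threshold, and it has no bearing on the Grade 3 ceiling.

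**Conclusion.** The point holds in a narrow form, and its severity is minor. Both statements of the catch-all stop at Grade 3, and the AESI list omits encephalitis although Section 10.2 acts on it at any grade. Under the Master text alone, unlisted immune-related Grade 4 events that meet no seriousness criterion, and non-serious encephalitis of Grade 1-2 (or Grade 4), are neither AESIs nor SAEs. They miss the 24-hour report and, if they start after the REP, are not collected.

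Few events should be affected, and the fatal and serious ones are already captured. The conclusion assumes that some Grade 4 events are not serious, and that neither the Always Serious list nor a Module covers the events in question.

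**What to change.** In Section 5.2.6.1.3 and in the last row of Table 10.1: 1, replace the reference to a Grade 3 event with an event of Grade 3 or higher. While doing so, align the two statements: the table requires the physician to consider the event immune-related, and the sentence in 5.2.6.1.3 does not repeat that condition.

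Reconcile Table 10.1: 1 with Section 10.2 by adding encephalitis to the Neurologic row, which already applies at every grade. Check the result against the Always Serious list and the Module AESI definitions so that the sources agree.

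These are reporting changes only, and no treatment rule is altered. The cost is a few words in an amendment, a matching edit to the CRF completion guide and a few more expedited reports.
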